7.2.2 Other Assays or Procedures

7.2.2.1 Pharmacokinetic Assessments

Blood levels of AMO-01 will be assessed at four time-points; pre-infusion, approximately 2 hours and approximately 6 hours after the commencement of the infusion of the study medication, as well as approximately 1 hour after the cessation of administration of the study medication. The central tendency values (and ranges) for AMO-01 plasma concentrations and imputed exposures (AUC) will be measured.

7.2.2.2 Biomarker/Physiological Assessments

7.2.12 Eye-tracking time on relevant target

Eye tracking will utilize three tasks to measure attention in general and social attention specifically. (1) The Visual Paired Comparison task presents two identical stimuli (faces or patterns) side by side for familiarization. The familiar stimulus and a new stimulus are then paired on test and recognition is inferred from preferential looking to the new target. (2) The Gap-Overlap task measures the latencies of gaze shifts from a central fixation point to a peripheral target are under 2 conditions. During gap trials, the fixation cross disappears prior to the onset of the peripheral cue, whereas in the overlap condition, the fixation cross remains on the screen throughout the trial. Saccadic latencies are typically greater for overlap than for gap trials since the former requires disengagement of attention. Four squares that flicker from black to white are presented against a grey background. The target square flickers 180 degrees out-of-phase from the three distractors. Flickering occurs at 1 of 4 frequencies: 0.2, 0.5, 1, or 2 Hz. A preference for the target square indicates phase individuation, which is easier at slower frequencies. Participants are directed to look at a screen for approximately 10 minutes while images of human faces are presented and automated assessments of time spent looking at socially salient features of test images are recorded.

7.2.13 Auditory Event Related Potential (AERP)

AERPs are useful for characterizing early processing of auditory tones and habituation to rapidly repeated stimuli as in speech processing. Tones are presented in rapid succession (e.g., up to every 500 ms) and ERP components to both initial stimulus presentations and their habituation to subsequent stimuli (i.e., reduction in amplitude) are examined. Auditory gating waveforms have been well characterized across development (Milner at l., 2014; Tremblay et al., 2014; Magnee et al., 2011) and are comprised of a fronto-central peak 100 ms after the onset of the auditory stimulus (N_1) and a subsequent positive peak (P_2) reflecting activity in auditory cortex, mesencephalitic reticular activating system, planum temporale, and auditory association cortex (Crowley et al., 2004; Godey et al., 2001). The N_1 - P_2 complex reflects two distinct components: initial stimulus processing (N_1) and subsequent attention to and processing of stimulus information (P_2). P_2 also has been implicated in speech processing (Knowland et al., 2014; Klucharev et al., 2003) suggesting that its analysis may be important for understanding neurophysiological mechanisms associated with broader cognitive and language developmental dysfunctions. Recent AERP studies suggest that measures of auditory gating may provide a sensitive and selective probe of sensory physiology in neurodevelopmental disorders (Hall et al., 2009). Individuals with FXS, for example, show auditory hypersensitivities consistent with Fmr1KO mouse models of local-circuit hyper-excitability involving prolonged "UP" states in the gamma frequency range, decreased glutamatergic drive on fast-spiking GABAergic inhibitory neurons in sensory cortex, and heightened neurophysiological response to auditory stimuli (Rotschafer et al., 2013).

7.2.14 Visual Evoked Potential (VEP)

VEPs provide a noninvasive technique to evaluate the functional integrity of visual pathways in the brain from the retina to the visual cortex via the optic nerve/optic radiations. The VEP is recorded from the head's surface, over the visual cortex, and is extracted from ongoing EEG through signal averaging. VEPs reflect the sum of excitatory and inhibitory postsynaptic potentials occurring on apical dendrites (Zemon et al., 1986) which modulate excitatory and inhibitory signals received by the pyramidal cells. The major positive and negative peaks and troughs in VEP waveforms reflect different cellular events. The contrast-reversing checkerboard stimulus used in this study produces a positive peak at approximately 60 ms (P_0 or P_{60}), reflecting activation of the primary visual cortex from the lateral geniculate nucleus. A negative peak at approximately 75 ms (N_0 or N_{75}) reflecting depolarization and glutamatergic postsynaptic activity spreading to the superficial layers of primary visual cortex, and a positive peak at approximately 100 ms (P_1 or P_{100}) reflecting superficial hyperpolarization and GABAergic activity (Zemon et al., 1980). VEPs have been used in clinical trials; for example, an antiepileptic drug (gabapentin; Conte et al., 2009) and an infant formula (O'Connor et al., 2001); both received FDA approval based in part on positive findings from VEP studies. Data from ongoing clinical trials at Mount Sinai provide support for use of VEPs as a measure of treatment response.

7.2.15 Electroencephalography (EEG)

EEG is a non-invasive measure of brain activity. An array of 24 electrodes will be placed on the subject's head using a standard 10-20 configuration. The EEG recording will last for approximately 30 minutes and will include an assessment of the effects of intermittent photic stimulation. The EEG signals that are obtained will be amplified and sent to a recording computer for processing and on-line viewing using Nicolet Natus Software. The EEGs will be edited both through automatic artifact-detection software and hand-editing. The EEG findings for each subject will be summarized using the SCORE-EEG reporting format. Each report will include a description of modulators/procedures (e.g. intermittent photic stimulation), background activity (e.g. posterior dominant rhythm), interictal findings (e.g. epileptiform interictal activity, including spike and sharp waves), episodes (e.g. seizures), and clinically relevant confounds (EEG artifacts). Clinically relevant screenshots will also be included in the SCORE-EEG report. A single clinician will review all processed EEGs and will render the summary of findings, the diagnostic significance, and clinical comments for each EEG tracing obtained from all subjects. EEGs will be obtained at Screening/V1, and at Follow-up1/V3, Follow-up 2/V4 and again at Follow-up 3/V5.

Clinically relevant EEG findings at Screening, V3, V4 and V5 will be listed for each subject and clinically relevant changes (e.g. in the frequency and prevalence of abnormal interictal activity) will be summarized at each assessment time point.

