4.1 Description of the Study Design

This is an open-label study to investigate the safety, tolerability and efficacy of a single 6-hour intravenous infusion of AMO-01 to treat adolescents and adults with PMS and co-morbid epilepsy. The subjects in this study will be administered the experimental study medication and then be followed up to ascertain safety and tolerability, and to determine whether their seizure frequency, as well as their signs and symptoms of PMS, are improving, using a caregiver-completed seizure diary as well as accepted rating scales and functional measures in addition to clinical EEG. Approximately 15 subjects will be screened and up to 10 subjects will receive study medication.

The study will have 4 phases (Figure 1, Study Design):

- Screening (Weeks -4 to -1): Subjects will be screened to ensure adherence to eligibility criteria and to assess pre-medication seizure frequency
- Baseline (Day 0): Subjects will complete baseline assessments in-clinic prior to study drug administration
- Study Drug Administration (Day 0): Eligible subjects will receive a single 6-hour intravenous infusion at a single dose of 120 mg/m²
- Follow-up (+1 day Week 8): follow-up visits will occur at 1 day after and 1, 2 and 4 weeks after receiving study medication. A phone call will occur 8 weeks after receiving study medication.

• .

Figure 1: Study Design

V	1	V2	V3	V4	V5	V6	Phone FU
- 1		Baseline					
	Week -4 to -1	Day 0 Study Drug	Day 1	Week 1	Week Z	Week 4	Week 8
	Screening	Administration Single 6-hour IV Infusion dose of 120mg/m ²			Follow-up		

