10.2 Statistical Hypotheses

We hypothesize that the medication will be safe and tolerable as determined by the absence of SAEs and propose that at least 70% of participants enrolled will be able to complete the infusion.

We hypothesize that, when relevant, seizures will be reduced in frequency by at least 25% compared with 'baseline.' More explicitly, the null (H0) and alternative (Ha) hypothesis will be defined as

H0: The average number of weekly seizures at follow-up (week 4) are reduced by less than 25% compared to baseline

Ha: The average number of weekly seizures at follow-up (week 4) are reduced by at least 25% compared to baseline

We hypothesize that EEG abnormalities will be reduced in frequency by at least 25% compared with 'baseline.' More explicitly, the null (H0) and alternative (Ha) hypothesis will be defined as

H0: The average number of EEG abnormalities at follow-up (week 2) are reduced by less than 25% compared to baseline

Ha: The average number of EEG abnormalities at follow-up (week 2) are reduced by at least 25% compared to baseline

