10.6.1 Enrollment/ Randomization/ Masking Procedures

Not Applicable

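### No masking is specified for the single EEG reader, so reader expectation could contribute to an apparent fall in EEG abnormalities

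*Combined protocol and SAP*

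**What the plan says.** Section 4.1 sets the design: "This is an open-label study to investigate the safety, tolerability and efficacy of a single 6-hour intravenous infusion of AMO-01". There is no control arm.

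Section 7.2.15 gives all EEG judgements to one person: "A single clinician will review all processed EEGs and will render the summary of findings". The same person also rates diagnostic significance and adds clinical comments. On timing it states: "EEGs will be obtained at Screening/V1, and at Follow-up1/V3, Follow-up 2/V4 and again at Follow-up 3/V5". Artefact removal is partly automatic and partly by hand; who does the hand-editing is not stated. Reports follow the SCORE-EEG format.

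Section 10.2 states the alternative hypothesis: "The average number of EEG abnormalities at follow-up (week 2) are reduced by at least 25% compared to baseline". Reducing EEG abnormalities is also a secondary objective in Section 3, while Section 4.2.3 and the Synopsis list EEG among the exploratory endpoints.

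Section 10.6.1, headed "Enrollment/ Randomization/ Masking Procedures", is marked not applicable. Section 10.6, on minimising bias, deals only with recruitment.

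**The concern.** A reader who can see the visit label knows treatment status: the V1 tracing is pre-dose, and those from V3, V4 and V5 are post-dose in every treated subject. Judgement enters in the hand-editing, in calling interictal findings, and in rating their diagnostic significance. The hypothesis points one way. If expectation lowers the post-dose calls, it does so in the hypothesised direction. With one reader for all tracings, a consistent tendency would not average out over ten subjects.

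The open-label design does not make this unavoidable. A caregiver who keeps a seizure diary cannot be masked here, but a stored recording can be read without its label. The plan does not use that protection for an outcome that has its own objective and its own hypothesis.

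**Working it through.** **Is the visit hidden anywhere?**
- Section 7.2.15 describes the recording, editing, report format and reader. It does not mention concealing date, visit or order.
- Section 10.6 covers recruitment only. Sections 10.6.1 to 10.6.3 are each marked not applicable.
- Section 10.1 leaves analysis detail to a separate SAP. The text available contains no rule on EEG reading.

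No sentence says that the reader knows the visit. The supported statement is that masking of the reader is not specified.

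**Is there a figure to reproduce?** No. Section 10.5 gives no statistical basis for the sample size, and the documents give neither a variance for EEG counts nor a size for reader bias. What follows is illustration.

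**Inputs from the documents:** n = 10 treated (upper limit, Section 4.1); Wilcoxon signed-rank test, two-sided 5% (Section 10.4).

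**Assumptions:** the test is applied at week 2 to d = log(week-2 count / Screening count). (Section 10.4 names week 1 and week 4 for the general test, and the log scale for seizures only.) The true drug effect is zero. d is normal with SD 0.3, 0.5 or 0.8. The reader under-scores post-dose files by a fraction b in every subject.

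**Method:** d ~ N(log(1 − b), SD²); for b = 0.20 the shift is log 0.80 = −0.223. With n = 10 the test rejects for a fall when W+ ≤ 8 (exact two-sided level 0.0488, so 0.0244 in that direction). The estimate is Hodges–Lehmann, back-transformed. There were 20,000 simulated trials per setting (standard error at most √(0.25/20,000) = 0.0035).

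Results at SD 0.3 / 0.5 / 0.8:

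| Under-scoring b | Significant fall | Point estimate shows fall ≥25% | Upper limit ≤0.75 |
|---|---|---|---|
| 0 | 2.5 / 2.5 / 2.7% | 0.2 / 3.9 / 13.6% | 0.0 / 0.0 / 0.1% |
| 10% | 16.5 / 8.5 / 5.6% | 3.1 / 12.9 / 24.9% | 0.0 / 0.1 / 0.5% |
| 20% | 53.8 / 23.0 / 11.5% | 25.5 / 33.8 / 39.6% | 0.5 / 1.1 / 1.4% |
| 30% | 90.3 / 50.5 / 23.2% | 75.8 / 66.6 / 60.4% | 9.1 / 5.4 / 4.2% |

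The last column is the rule that Section 10.4 states for seizures. No rule is stated for EEG.

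**With masking.** Suppose the reader under-scores by 30% any file believed to be post-dose, and guesses the visit correctly with probability q. The chance of a significant fall, in the same SD order, is:
- q = 0.5 (masking holds): 2.6 / 2.6 / 2.3%
- q = 0.6: 7.5 / 5.4 / 4.2%
- q = 0.7: 19.1 / 10.6 / 7.1%

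**Workload:** 10 subjects × 4 EEGs = 40 recordings; 40 × 0.5 h = 20 h of tracing.

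**The case against.** The entry in Section 10.6.1 most naturally refers to masking of treatment in an open-label trial. It does not forbid masked reading, and a reader might wrongly infer from it that the EEG reader certainly sees the visit. The documents do not say so. This stands, and is why the point is put as masking not specified.

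EEG is an exploratory endpoint, Section 7.2.15 plans listings and summaries, and the primary endpoints are safety. This also stands and limits the consequence. It does not cancel the point, because Section 10.2 attaches a directional 25% hypothesis to the reader's findings.

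One reader for all files, a structured report and automatic artefact detection limit variability. They deserve credit, but none of them conceals the visit.

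It is also tempting to infer that expectation alone would deliver the hypothesised 25% fall. The documents give no bias figure. In the illustration, 20% under-scoring would meet a rule like the one for seizures in only 0.5% to 1.4% of null trials. The excess of apparent 25% falls must be read against the zero-bias row, which already reaches 13.6% at SD 0.8.

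Finally, recoding files does not guarantee masking. Coding after hand-editing would leave the editing open to influence, and a scorer who has already read the labelled tracings may recognise them. The fix has to meet both points.

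**Conclusion.** The point holds in a limited form. The plan specifies no masking of the single EEG reader to visit, date or order, for an outcome that rests on judgement and has a directional hypothesis in an open-label trial. Reader expectation could contribute to an apparent fall.

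Its size is unknown. On the assumed SDs and a uniform 20% under-scoring, a nominally significant fall would appear in about 12% to 54% of trials with no drug effect, against about 2.5% without bias. These figures depend wholly on the assumptions, and the conclusion does not need them.

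This should be corrected, but it is not critical, because EEG is listed as exploratory. Masked reading would not make a before-after fall attributable to the drug: regression to the mean, one pre-dose recording of about 30 minutes, and the absence of a control arm would all remain.

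**What to change.** Add the following to Section 7.2.15:

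1. Before hand-editing, existing study staff other than the reader strip date, visit and annotations from each recording, assign a random code and hold the key. If editing must come first, it follows a fixed written rule.
2. The same single clinician scores all coded files in random order, preferably in one batch across subjects at the end. With only four files per subject, scoring subject by subject makes recognition easier.
3. Only these scores are used for the EEG endpoint and the 25% hypothesis.
4. Any reading needed for care at a visit stays separate and is not analysed. Where possible it is done by the usual clinical reader and not by the endpoint scorer.

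The cost is relabelling, later endpoint scores, and possibly a second pass over at most 40 recordings. No planned step is delayed: EEG findings are not an eligibility criterion (Sections 5.1 and 5.2), no interim analysis is planned (Section 10.4.7), and analysis waits for database lock (Section 10.3). The documents do not settle who is available to hold the key, so the sponsor should confirm this.

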7.2.2.3 Change in phosphorylated ERK levels

Samples of 6 ml blood will be taken pre-infusion, approximately 2 and 6 hours after the start of the infusion, approximately 1 hour after the cessation of the infusion, and at the 1 week (V4) and 4 week (V6) visits. The sample will be provided as whole blood with fixative, to be used for the analysis of levels of phosphorylated ERK and total ERK protein.

7.2.3 Specimen Preparation, Handling and Storage

7.2.3.1 PK

Instructions for collection, handling, storage, processing and shipment of the PK sample will be provided in a separate laboratory manual.

7.2.3.2 pERK

Instructions for collection, handling, storage, processing and shipment of the pERK sample will be provided in a separate laboratory manual.

7.2.4 Specimen Shipment

7.2.4.1 PK

Instructions for collection, handling, storage, processing and shipment of the PK sample will be provided in a separate laboratory manual.

7.2.4.2 pERK

Instructions for collection, handling, storage, processing and shipment of the pERK sample will be provided in a separate laboratory manual.

7.3 Study Schedule

7.3.1 Screening

The Screening visit (V1) will occur in the 4 weeks preceding the Baseline visit (V2). Participants and their families will come in to sign the informed consent and meet with members of the study team. Refer to the schedule of events (Table 1) for the assessments to occur at the Screening visit (V1).

7.3.2 Enrollment/Baseline

If all eligibility criteria are met, the subject will be booked in for their Baseline visit (V2). Pre-infusion procedures as outlined in Table 2, schedule of events, will occur prior to the administration of AMO-01. Procedures outlined as 'during infusion' and 'post infusion' will occur during and after the administration of AMO-01, respectively. Table 2 outlines the procedures to be completed during and after AMO-01 administration.

7.3.3 Follow-up

Planned follow-up visits will occur at 1 day (V3), week 1 (V4), and week 2 (V5) post-dose. A follow-up phone call will occur 8 weeks post-dose. Refer to the schedule of events (Table 1) for a list of assessments to be completed at each follow-up visit.

7.3.4 Final In-Clinic Study Visit

A final in-clinic study visit (V6) will be conducted 4 weeks post-dose. Refer to the schedule of events (Table 1) for a list of assessments to be completed at this visit.

7.3.5 Early Termination Visit

In the event of early termination or withdrawal, the subject will complete the assessments scheduled for the final in-clinic study visit (V6). The follow-up phone call will also be attempted. Refer to the schedule of events (Table 1) for a list of assessments to be completed at this visit.

7.3.6 Unscheduled Visit

Unplanned visits will be permitted if there are any concerns about safety and/or adverse events (AEs).

7.3.7 Schedule of Events Table

Refer to Table 1 and Table 2 for schedule of events.

7.4 Participant Access to Study Agent At Study Closure

As AMO-01 is not a marketed product and this study represents a pilot investigator led study, there will be no access to study agent at study closure.

7.5 Concomitant Medications, Treatments, and Procedures

Non-pharmacologic educational and behavioral interventions will be allowed. Subjects will be asked at the time of consent/assent to not change concomitant treatments for the duration of the study.

Concomitant medication will be allowed, providing that they have been stable for at least 1 month prior to Screening (V1) and every effort will be made for medications to continue to be stable during the study. Exceptions may be allowed if concomitant medication is required on a self-limited basis for the clinical management of adverse events (i.e. headache, infection).

Contraindicated medications include Coumadin or heparin administered within the two weeks prior to Screening (V1).

8 ASSESSMENT OF SAFETY

8.1 Specification of Safety Parameters

8.1.1 Definition of Adverse Events (AE)

An adverse event (AE) will be defined as any untoward medical occurrence in a study subject, temporally associated with the use of the experimental medication, whether or not considered related to the medication. An adverse event can therefore be any unfavorable and unintended sign (including an abnormal laboratory finding), symptom, or disease (new or exacerbated) temporally associated with the use of the experimental medication.

8.1.2 Definition of Serious Adverse Events (SAE)

A serious adverse event (SAE) will be defined as an AE that meets any of the following criteria:

- results in death;
- is life threatening;
- requires inpatient hospitalization;
- results in a persistent or significant disability/incapacity;
- any other adverse event that, based upon appropriate medical judgment, may jeopardize the subject's health and may require medical or surgical intervention to prevent one of the outcomes listed above.

8.1.3 Definition of Unanticipated Problems (UP)

Unanticipated problems will be defined by three criteria:

- 1. The AE is unexpected (see section 8.2.3);
- 2. The AE is possibly related to participation in the research (see 8.2.2.);
- 3. The AE suggests that the research places subjects or others at a greater risk of harm than was previously known or recognized.

8.2 Classification of an Adverse Event

8.2.1 Severity of Event

Monitoring for AEs will be conducted during scheduled and unscheduled visits per clinical and laboratory assessments. General AEs will be graded by the National Cancer Institute (NCI) CTCAE scales. Any AE that the PI deems serious, although not easily categorized in the National Cancer Institute grading system, will be considered \geq grade 3. If a subject develops significant (CTCAE AE \geq 3 grade) neurological signs and

symptoms (e.g. cerebrovascular event or peripheral neuropathy), they will be seen immediately for a comprehensive evaluation, appropriate treatment, and removal from active participation in the study.

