5.4 Participant Withdrawal or termination

5.4.1 Reasons for Withdrawal or Termination

If a subject is discontinued at any time after Baseline (V2), the investigator will make every effort to see the subject and complete the final in-clinic study visit (V6) as soon as possible, ideally within one week of discontinuation of the other scheduled study procedures. A follow-up telephone call will still be attempted 4 weeks later.

Subjects may withdraw from the study at any time without stating a reason and without prejudice to further treatment. The Investigator may withdraw a subject from the study and discontinue study treatment and assessments at any time.

Early discontinuation of any subject who has given informed consent to participate will be recorded including the reason for discontinuation. The primary reason for a subject withdrawing prematurely will be selected from the following standard categories of early discontinuations:

- Failed to meet enrollment criteria.
- Adverse Event: Clinical events occurred or laboratory results are reported that in the medical judgment of the investigator are grounds for discontinuation in the best interests of the subject.
- Withdrawal of Consent: The subject desired to withdraw from further participation in the study. The subject is not obliged to provide any reason for withdrawal of consent, but where a reason is given this will be recorded on the CRF.
- Protocol Violation: The subject failed to adhere to the protocol requirements, at the investigator's discretion
- Lost to Follow-Up: The subject stopped coming for visits and study personnel were unable to contact the subject or caregiver. Every effort should be made to re-contact the subject prior to declaring a subject as lost to follow-up, which must be at least 3 documented attempts. The 3rd must be in writing and confirmed to have been received (e.g. registered post).
- Other: The subject was terminated for a reason other than those listed above, such as termination of study.

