5.4.2 Handling of Participant Withdrawals or termination

If a subject is withdrawn from active study during screening or observation phases of the study, they will be returned to the referring physician and standard care will be recommended; in addition we will request the subject's participation in an end-of-study visit.

If a subject is withdrawn from active study during active treatment, they will also be returned to the referring physician and standard care will be recommended; however, in this case, we will in addition

request the subject's participation in clinical and laboratory safety assessments and follow up per protocol schedule.

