5.5 Premature Termination or Suspension of Study

The following criteria will be used to identify possible adverse treatment events, which will indicate the need to halt active participation of the subject:

- Withdrawal of Consent
- PI or any regulatory authority (Safety Monitoring Board, IRB) believe withdrawal is necessary for the subject's health, well-being, or best interests.
- Any serious related AE of any sort (clinical, laboratory) \geq 4 will result in halting for the individual and also for the study as a whole.

Return of a subject to active study participation will not be permitted, except if a transient clinical or laboratory abnormality unrelated to study treatment has occurred and subsequent permission of the Safety Monitoring Board to return the patient to active study has been provided.

If a subject is withdrawn from active study during screening or observation phases of the study, they will be returned to the referring physician and standard care will be recommended; in addition we will request the subject's participation in an end-of-study visit

If a subject is withdrawn from active study during treatment, they will also be returned to the referring physician and standard care will be recommended; however, in this case, we will request the subject's participation in clinical and laboratory safety assessments and follow up per protocol schedule.

The study will be halted* if two patients experience stopping conditions across sites. (Exceptions for this criterion: Patients who withdraw voluntarily for reasons not directly related to or intrinsic to the study, e.g. incidental considerations such as concerns about travel time to study visits, unexpected pregnancy in the family, etc. In addition, the study will be halted if one patient experiences a serious related adverse effect (grade \geq 4 AE).

All safety data will be reported to the Safety Monitoring Board and IRB every six months, or, in the case of any major safety concern or question, immediately. If any study stopping condition occurs, this will be reported immediately and the study halted, pending review by the Safety Monitoring Board and IRB, and until the decision by regulatory authorities to resume, suspend or close the study has been made.

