8.5 Study Halting Rules

As indicated in the Synopsis, the following criteria will be used to identify possible adverse treatment events, which will indicate the need to halt active participation of the subject in the study:

- Withdrawal of Consent
- PI or any regulatory authority (DSMB, IRB, or FDA) believe withdrawal is necessary for the subject's health, well-being, or best interests.
- PI or any regulatory authority believe that withdrawal is necessary for the subject's health, well-being, or best interests
- Laboratory: any abnormality on any test with adverse event (AE, Common Terminology Criteria for Adverse Events, National Cancer Institute, scales) ≥ 3 or greater at any time in the study
- Any AE of any sort (clinical, laboratory) \geq 4 will result in halting for the individual and also for the study as a whole.

To avoid bias, all analyses will include all subjects, including those withdrawn from the study, regardless of adherence to study protocol. Especially in a phase I/II of exploratory trial of a novel, unproven treatment, the safety of subjects must be the primary *overriding* concern. If there is doubt concerning a subject's safety, the default mode must be withdrawal from treatment or active study participation, followed by close observation (safety follow up visits) and recommendation of standard treatment.

If a subject is withdrawn from active study during screening or observation phases of the study, they will be returned to the referring physician and standard care will be recommended; in addition we will request the subject's participation in an end-of-study visit, as per the schedule of the part of the study.

If a subject is withdrawn from active study during treatment, they will also be returned to the referring physician and standard care will be recommended; however, in this case, we will in addition request the subject's participation in clinical and laboratory safety assessments and follow up per protocol schedule.

Stopping Conditions for Study as a Whole

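### Removing a dosed subject after a severe event stops no drug but may cost the Week 4 data, and the call tied to an early V6 falls before Week 8

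*Combined protocol and SAP*

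**What the plan says.** Treatment is a single infusion on Day 0 (Section 6.1.5). Two grade-based rules end a subject's active participation. Section 8.2.1 says of anyone with grade 3 or worse neurological signs that "they will be seen immediately for a comprehensive evaluation, appropriate treatment, and removal from active participation in the study". Section 8.5 lists, among the reasons to halt a subject, "Laboratory: any abnormality on any test with adverse event (AE, Common Terminology Criteria for Adverse Events, National Cancer Institute, scales" at grade 3 or above. Neither rule requires the event to be related to treatment. The way back is narrow: "Return of a subject to active study participation will not be permitted, except if a transient clinical or laboratory abnormality unrelated to study treatment" is the reason, and then only with permission from the Safety Monitoring Board (Section 5.5).

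For a subject discontinued after Baseline, Section 5.4.1 has the investigator try to "complete the final in-clinic study visit (V6) as soon as possible, ideally within one week of discontinuation of the other scheduled study procedures", and adds: "A follow-up telephone call will still be attempted 4 weeks later". Section 7.3.5 also places the V6 assessments at early termination. The diary is collected at V6 (Section 7.1.8), and V6 is the last visit with rating scales (Table 1).

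On analysis, Section 8.5 commits as follows: "To avoid bias, all analyses will include all subjects, including those withdrawn from the study, regardless of adherence to study protocol". The seizure hypothesis in Section 10.2 is set at Week 4. The primary adverse-event endpoint in Section 4.2.1 runs to Week 8. Section 10.4.5 expects no major difficulty with missing values.

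**The concern.** In a repeated-dose trial, taking a subject off after a severe event protects the subject by stopping exposure. Here exposure is over within six hours. Removal in the following weeks leaves no dose to withhold, and all it can change is how long and how closely the subject is observed.

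Two things are at stake. First, at most 10 subjects are dosed and the seizure hypothesis and the later scale comparison are fixed at Week 4, so each missing Week 4 value counts, and the commitment in Section 8.5 cannot be met with data that were never collected. Second, the subjects affected are those who had a severe event. For them, sites hold two different dates for the last safety contact.

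**Working it through.** The plan gives no figure to reproduce: Section 10.5 calls the sample size pragmatic. The check is a comparison of sections, followed by day arithmetic.

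**1. Which rule governs a removed subject**

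- Sections 5.4.1 and 7.3.5: V6 assessments early. Section 5.4.1 puts the call 4 weeks later; 7.3.5 says the call will be attempted and refers to Table 1, which shows Week 8.
- Sections 5.4.2, 5.5 and 8.5, withdrawal in the observation phase: an end-of-study visit is requested. Section 8.5 alone adds that this follows the schedule for that part of the study.
- Section 5.4.2 (with parallel text in 5.5 and 8.5): "If a subject is withdrawn from active study during active treatment", safety assessments and follow-up on the protocol schedule are requested. Active treatment here lasts six hours.
- Section 8.5, in case of doubt about safety: "the default mode must be withdrawal from treatment or active study participation, followed by close observation (safety follow up visits" and so on, with no dates.

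None of these expressly keeps the diary or the scales going after an early V6. They also do not agree on when the end-of-study visit takes place.

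**2. Dates**

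Inputs: planned V6 on Day 28 and call on Day 56 (Sections 7.3.4 and 4.1); early V6 within 7 days of removal and call 28 days later (Section 5.4.1). Let removal be on day d and the early V6 on day v, with v from d to d+7, capped at 28.

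- Diary days lost if the diary ends at V6 = 28 − v
- Call day = v + 28
- Shortfall against Week 8 = 56 − (v + 28) = 28 − v

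| Removal day | V6 day | Diary days lost (of 28) | Call day | Days short of Day 56 |
|---|---|---|---|---|
| 1 | 1–8 | 20–27 | 29–36 | 20–27 |
| 7 | 7–14 | 14–21 | 35–42 | 14–21 |
| 14 | 14–21 | 7–14 | 42–49 | 7–14 |
| 21 | 21–28 | 0–7 | 49–56 | 0–7 |

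If the 4 weeks are counted from discontinuation instead of from V6, the shortfall is 28 − d, the upper end of each range. The call reaches Day 56 only if V6 is on Day 28.

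**3. Can an early V6 stand in for Week 4?**

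The ABC (Appendix E) asks about the previous four weeks, so at an early V6 on day v, 28 − v of its 28 days lie before dosing. For removal on Day 1 that is 20/28 to 27/28, or 71–96%; on Day 7 it is 50–75%. The telephone question in Section 7.1.15 compares seizures with the Week 4 record, which a removed subject may not have.

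**4. Seizure ratio, illustration only**

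The documents give no removal rate, no SD of the log-ratio, and no correlation between removal and seizure change. All three are assumed here, with no true effect, and removed subjects are left out. If the subject with the highest removal score is lost from 10, the mean log-ratio of the other nine shifts by −r × SD × 1.539 / 9, where 1.539 is the expected maximum of 10 standard normal values.

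- r = 0: ratio 1.00, no bias.
- SD 0.6, r = 0.25: exp(−0.0256) = 0.975.
- SD 0.6, r = 0.5: exp(−0.0513) = 0.950.
- r = 0.5, SD from 0.4 to 1.0 (simulated): 0.97 to 0.92.
- Two lost, SD 0.6, r = 0.5 (simulated): 0.909. This needs the study to resume after the halt that two stopping conditions trigger.

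The criterion in Section 10.4, an upper confidence limit at or below 0.75, was met in at most 0.96% of simulated trials in any setting (SD 1.0, r = 0.5, two lost).

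**The case against.** The strongest reply is that the sections are ambiguous rather than wrong. Section 8.2.1 does not point to 5.4.1. Section 8.5 can be read as leaving the end-of-study visit at its scheduled time. Unscheduled visits for safety concerns are allowed (Section 7.3.6). This stands. A reader might infer that the diary and scales definitely stop at removal, but no sentence says so. What the text supports is that nothing expressly continues them and that the rules conflict.

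On the call, several sections (4.1, 6.1.9, 7.3.3 and 8.3) and Table 1 put it at 8 weeks, against one sentence in 5.4.1. That sentence is nevertheless the one written for discontinued subjects. A reader might infer that adverse events after an early call go unrecorded. Section 8.3 sets recording up to the 8-week call, so the documents show a conflict of dates and not a loss of events.

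The recall overlap in the ABC is not peculiar to removal. At the planned Week 1 visit it is already 21/28 = 75% for every subject. This too stands: the overlap shows only that an early V6 is not a Week 4 measurement.

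Finally, efficacy is secondary, and Section 10.1 defers details to a separate SAP that is not in the text reviewed. That SAP could say how an early V6 is used, and average weekly seizures could be computed from the diary days available. It could not supply Week 4 data that nobody collected.

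**Conclusion.** The point holds as a real inconsistency in what happens to a dosed subject after removal. Sections 5.4.1 and 7.3.5, followed as written, bring V6 forward, may leave no true Week 4 data for subjects whom 8.5 includes in all analyses, and, under 5.4.1, place the call before Week 8 whenever V6 is early. For removal between Day 1 and Day 14 the call shortfall is 7–27 days. This assumes that the one-week target for V6 is met.

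A reader might conclude that the seizure result is biased toward benefit. The documents do not support this. The examples in 8.2.1 are a cerebrovascular event and peripheral neuropathy, and the other trigger is a laboratory value; nothing ties either to seizure change. The illustrative ratios depend wholly on assumed inputs and on leaving removed subjects out, which 8.5 says will not be done. Size and direction cannot be derived, and under the assumptions tried the effect on the 0.75 criterion is negligible. The case rests on avoidable loss of data among at most 10 subjects and on contradictory last-contact dates.

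**What to change.** State in Sections 5.4.1, 5.4.2, 5.5, 7.3.5, 8.2.1 and 8.5 that every dosed subject whose family agrees continues the diary and the remaining visits through V6 on the original schedule, with the call at Week 8 post-dose, whatever the participation status. If an early V6 cannot be avoided, keep the call at Week 8 post-dose and analyse that visit by its actual study day, not as Week 4.

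The removal criteria themselves need not change. The cost is protocol wording plus some visits, already in the schedule, for subjects who may be unwell; family agreement limits that burden.
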